### **2.3. Randomization and Masking**

Children meeting inclusion criteria will be enrolled by local trained study personnel. At enrollment, children will be assigned a study identification number using the next unassigned number on a list identification numbers assigned to the site. Enrolled children will then undergo a baseline assessment. The baseline assessment includes data collection on demographics and socioeconomic status, anthropometric assessments, and a malaria rapid diagnostic test (RDT; see Figure 1 and Section 3 for details). After completion of the baseline assessment,

children will be randomized to receive either a single dose of directly observed oral azithromycin or a 7-day course of oral amoxicillin.

The randomization sequence will be generated by the UCSF investigators using R (R Foundation for Statistical Programming, Vienna, Austria). Children will be randomized in a 1:1 fashion to a single dose of azithromycin or a short course of oral amoxicillin. The randomization sequence will be linked to the study identification numbers. Randomized study arm assignments will be placed in sealed, opaque envelopes labeled with study identification numbers. When a child has been enrolled and has completed the baseline assessments, a CSPS nurse trained for the study will open the envelope to determine the allocation, and will administer study medication indicated as described in Sections 2.4 and 4.

To keep the allocation concealed, only the study nurse administering treatment will have access to the envelopes with the randomization allocations. The study nurse will open the envelope and administer treatment in a private room without the outcome assessor present. For each enrolled child, the study nurse will record whether or not azithromycin was administered on a paper form kept in a locked cabinet not accessible by the outcome assessor.

Given the nature of the intervention, participants and study personnel administering treatment will not be masked to treatment assignment. Outcome assessors will be masked to treatment assignment; this will be accomplished by assigning one CSPS nurse to administer treatment and a separate masked study team member to perform outcome assessments, including anthropometry, malaria RDT, and vital status updates.

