### Secondary Outcomes

- **Nutritional recovery by 8 weeks (Specific Aim 2).** Nutritional recovery will be defined as a child having WHZ  $\geq -2$  on two consecutive visits and no acute complication or edema for the past 7 days OR MUAC of  $\geq 125$ mm on 2 consecutive visits and no acute complication or edema for the past 7 days. The criteria chosen to define the recovery will be the same one we used to admit the child into the program.

- **Time to recovery.** Time from enrollment to nutritional recovery (defined above) will be calculated in days by subtracting the date of enrollment from the date of nutritional recovery.
- **Nonresponse at 8 weeks.** Nonresponse will be documented if a child does not meet the criteria for nutritional recovery at 8 weeks.
- **Transfer to inpatient care.** The occurrence, date, and reason for transfer from outpatient to inpatient treatment will be recorded.
- **Mortality by 8 weeks.** Vital status will be assessed at all follow-up time points and mortality will be defined as death during the study period. Date of death will be recorded.
- **Clinical signs of infection.** At all follow-up time points, clinical signs of infection will be recorded, including care-giver reported experience of fever, diarrhea, vomiting, and respiratory infection/cough and clinical diagnoses made at by site personnel
- **Adverse events.** Adverse events will be reported at all follow-up time points (defined in Section 5).
- **HAZ.** Height or length will be measured at all follow-up time points and height-for-age z-scores will be calculated.
- **MUAC.** Mid-upper arm circumference will be measured at all follow-up time points.
- **WAZ.** Weight will be measured at all follow-up time points and weight-for-age z-scores will be calculated.
- **WHZ.** Weight and height, assessed at all follow-up time points, will be used to calculate weight-for-height z-scores.
- **Malaria.** Rapid diagnostic tests for malaria will be conducted at baseline and week 8 to determine malaria infection status.
- **Intestinal microbiome:** Rectal swabs will be collected in a random subset of children at baseline and at week 8.

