### 3.3. Malaria Rapid Diagnostic Test

[figure not shown]
Malaria infection status will be assessed on all enrolled children using a rapid diagnostic test (RDT) at baseline and 8 weeks after admission into the nutritional program. At this point, we will also take the child's temperature.

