### 9.2. Statistical Analysis

**Baseline characteristics.** Characteristics of the study population collected at baseline will be summarized using frequencies and percentages for categorical variables and means and standard deviations or medians and inter-quartile ranges for continuous variables. Baseline characteristics will be compared by treatment arm using Fisher's exact test for categorical variables and t-tests or Wilcoxon rank-sum tests for continuous variables.

**Specific Aim 1.** The primary analysis will compare weight gain velocity (g/kg/day) between groups over the 8-week follow-up period,. We will estimate mean differences and 95% confidence intervals for the difference using a linear regression model with an indicator for study group.

$$E[Y | X = x] = \beta_0 + \beta_1 X + e$$

Where:

- $Y$  = weight gain velocity from enrollment to 8 weeks
- $X$  = binary indicator for treatment group ( $X=1$  for azithromycin,  $X=0$  for a short course of oral amoxicillin)
- $\beta_1$  = difference in weight gain velocity between the azithromycin group compared to a short course of oral amoxicillin group

- $e \sim N(0, \sigma^2)$

**Specific Aim 2.** The primary analysis will compare nutritional recovery by 8 weeks from baseline by arm. We will use log-binomial regression for this analysis to estimate the risk ratio. We will use the following model:

$$\log[P(Y = 1|X_1 = x_1)] = \beta_0 + \beta_1 X_1 + e$$

Where:

- $Y$  = binary indicator for nutritional recovery by 8 weeks ( $Y=1$  for recovered,  $Y=0$  for not recovered)
- $X$  = binary indicator for treatment arm ( $X=1$  for azithromycin,  $X=0$  for a short course of oral amoxicillin)
- $e^{\beta_1}$  = relative risk of nutritional recovery in azithromycin arm compared to a short course of oral amoxicillin arm
- $e \sim N(0, \sigma^2)$

If the log-binomial model fails to converge, we will use a modified Poisson model with robust standard errors as an alternative.

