### **Secondary outcomes.**

Time to event outcomes (time to recovery and time to mortality) will be assessed visually using Kaplan-Meier curves and compared by arm using the log-rank test.

Binary outcomes will be analyzed using modified Poisson regression for rare outcomes (e.g. mortality) or log-binomial regression for common outcomes (e.g. malaria), using models similar to the one described above for Specific Aim 2.

Anthropometric assessments will be analyzed using linear models as described for Specific Aim 1, with correction for baseline values. For anthropometric assessments, z-scores will be calculated based on the 2006 WHO Child Growth Standards. Anthropometric z-scores will be analyzed as continuous variables and secondary analyses will explore categorization.

All analyses will be intention-to-treat. A significance level of 0.05 for inference and 95% confidence intervals will be reported for all effect estimates. All analyses will be conducted using R (R Foundation for Statistical Computing, Vienna, Austria). For all models, model diagnostics will be conducted to assess appropriate fit.

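### The week-8 malaria comparison leaves out the baseline rapid test that every child has before allocation; adding it is a free, probably modest, gain in precision.

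*Combined protocol and SAP*

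**What the plan says.** Section 2.5 lists malaria as a secondary outcome: "Rapid diagnostic tests for malaria will be conducted at baseline and week 8 to determine malaria infection status". Section 3.3 confirms the coverage: "Malaria infection status will be assessed on all enrolled children using a rapid diagnostic test (RDT) at baseline and 8 weeks after admission".

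The baseline test comes before treatment is known. In Section 2.3, "The baseline assessment includes data collection on demographics and socioeconomic status, anthropometric assessments, and a malaria rapid diagnostic test", and then "When a child has been enrolled and has completed the baseline assessments, a CSPS nurse trained for the study will open the envelope".

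For the analysis, Section 9.2 (Secondary outcomes) assigns "log-binomial regression for common outcomes (e.g. malaria), using models similar to the one described above for Specific Aim 2". The Aim 2 text it points to says "We will use log-binomial regression for this analysis to estimate the risk ratio", and the only regressor defined there is a "binary indicator for treatment arm".

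The next paragraph of the same section treats growth measures differently: "Anthropometric assessments will be analyzed using linear models as described for Specific Aim 1, with correction for baseline values". No corresponding statement is made for malaria.

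**The concern.** A child who tests positive at entry may well have a different chance of testing positive at week 8. If so, baseline status explains part of the outcome variance, and a model with arm alone leaves that part in the error. Two things follow. The confidence interval is wider than the data require. And if the arms happen to differ in baseline positivity, the point estimate is pulled in that direction.

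The plan has no other device that deals with this. Section 2.3 describes 1:1 allocation and states no stratification. Section 9.2 tests baseline characteristics between arms, but no adjustment follows from those tests. The inverse probability weights under Missing data use SES, distance, WHZ and MUAC, not the RDT, and apply only as a sensitivity analysis when more than 10% of outcomes are missing. If the baseline table did show an RDT imbalance, the analyst would have no planned response, and adjusting after seeing it would be open to challenge.

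**Working it through.** **Inputs from the documents.** 300 children, 150 per arm, 10% loss (Section 9.1), so 135 per arm with week-8 data. Alpha is 0.05.

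**The plan's own figure.** No power statement is made for malaria. The Aim 2 statement, whose model malaria borrows, reproduces. For 66% against 81%, n per arm = [1.96·√(2·0.735·0.265) + 0.8416·√(0.66·0.34 + 0.81·0.19)]² / 0.15² = (1.2233 + 0.5177)² / 0.0225 = 134.7, that is 135; and 135/0.9 = 150.

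**Assumed inputs.** The documents give neither malaria prevalence nor the link between the two tests. Let pb be baseline positivity, and p1 and p0 week-8 positivity in baseline positives and negatives, with p = pb·p1 + (1−pb)·p0.

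**Precision.** R² = 1 − [pb·p1(1−p1) + (1−pb)·p0(1−p0)] / [p(1−p)]. The gain in equivalent sample size is 1/(1−R²) − 1.

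- Weak link, pb 0.5, 35% vs 25%: R² = 1 − 0.2075/0.2100 = 1.2%, worth 1.2% more children.
- Lower end of the stronger setting, pb 0.4, 45% vs 20%: R² = 1 − 0.1950/0.2100 = 7.1%, worth 7.7%.
- Upper end, pb 0.4, 60% vs 15%: R² = 1 − 0.1725/0.2211 = 22.0%, worth 28.2%.

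For two binary variables R² is φ², the squared correlation between the tests. The variance ratio (adjusted to unadjusted) is therefore 1 − φ², the interval narrows by 1 − √(1−φ²), and the equivalent total is 270/(1−φ²). The simulated column compares the unadjusted log risk ratio with a baseline-stratified Mantel-Haenszel one, with no true effect, 135 per arm and 3,000 trials per setting. The power column takes a difference with 80% power unadjusted (assumed 30% vs 15.7%) and uses 135/(1−φ²) per arm.

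| φ | Variance ratio | Interval narrower by | Equivalent N | Simulated ratio | Power |
|---|---|---|---|---|---|
| 0 | 1.00 | 0% | 270 | about 1.00 | 80.0% |
| 0.1 | 0.99 | 0.5% | 273 | 0.99–1.00 | 80.4% |
| 0.2 | 0.96 | 2.0% | 281 | 0.95–0.98 | 81.6% |
| 0.3 | 0.91 | 4.6% | 297 | 0.90–0.92 | 83.6% |
| 0.5 | 0.75 | 13.4% | 360 | 0.74–0.77 | 90.0% |

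**Chance imbalance.** SD = √(2·pb(1−pb)/135): 6.0 points at pb 0.4 and 6.1 at pb 0.5. The 95% range is ±9.5, ±10.9 and ±11.9 points at pb 20%, 30% and 50%, and the chance of more than 10 points either way is about 4%, 7% and 10%.

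**Effect on the estimate.** The unadjusted week-8 difference moves by the imbalance times (p1 − p0). For 10 points this is 10 × 0.25 = 2.5 to 10 × 0.45 = 4.5 points in the stronger setting; for a one-SD imbalance of 6 points it is 1.5 to 2.7. On the ratio scale, in the simulations, a 10-point imbalance multiplied the unadjusted risk ratio by 1.04–1.10 at φ 0.2, 1.06–1.17 at φ 0.3 and 1.11–1.28 at φ 0.5. The stratified ratio stayed at 0.99–1.01.

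**The case against.** The strongest reply is that nothing here is an error. In an individually randomized trial the unadjusted risk ratio is valid, and its interval already allows for chance imbalance. That stands: the point is about efficiency and about the estimate given the imbalance that occurs, not systematic bias.

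The size may also be small. Up to φ 0.3 the interval narrows by less than 5%. Section 3.6 records treatments given or recommended, and if children positive at entry are treated, the link to week 8 could weaken. A 10-point imbalance is also towards the tail. These points stand as limits on size. They do not argue against adjusting, since at φ = 0 the loss is negligible.

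The plan asks only for a model resembling the Aim 2 one, which does not forbid a covariate. But none is named, and baseline correction is written out for anthropometry alone, so the natural reading is arm only.

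Finally, a main-effect covariate assumes a common risk ratio in children positive and negative at baseline; if that fails, the adjusted ratio need not equal the marginal one. This is a fair but minor caveat. Where the common ratio holds, the risk ratio is collapsible and the quantity estimated does not change.

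**Conclusion.** The concern holds. As written, the week-8 malaria model has no baseline term, although a valid pre-allocation measurement exists for every child and the plan adjusts for baseline elsewhere. The loss runs from about 1% in sample-size terms with a weak link to 8–28% in the stronger setting. Both figures rest on assumed malaria rates, because the documents supply none. Consequence is low: malaria is one of 13 listed secondary outcomes in a pilot, is part of neither specific aim, and has no power calculation. It is worth doing because it costs almost nothing.

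**What to change.** In Section 9.2, Secondary outcomes, state that the week-8 malaria model includes the baseline RDT result (positive or negative) as a covariate alongside arm. State also that the modified Poisson model with robust standard errors, already named as the Aim 2 fallback, applies here if the log-binomial model does not converge. The unadjusted risk ratio can be reported beside it as a check.

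The cost is one line in the plan, made before outcome data are seen, and no new data. The drawbacks are a somewhat higher chance of needing the fallback model and the common-risk-ratio assumption.

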### **Missing data.**

If  $\leq 10\%$  of enrolled children is missing outcome data, complete case analyses will be conducted. If  $>10\%$  of enrolled children are missing outcome data, inverse probability weighting will be used to weight complete cases by the inverse of an estimate of the probability of an outcome being observed as a sensitivity analysis. Weights will be constructed with the following baseline characteristics chosen as factors likely to predict follow-up: SES, distance from CSPS, WHZ, and MUAC.

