## 2.5. Outcomes

### Primary Outcome

- **Weight gain over 8 weeks (Specific Aim 1).** Weight will be measured at all follow-up time points and weight gain will be defined as grams per kilogram per day (g/kg/day).

[figure not shown]

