## 9. STATISTICAL METHODS

### 9.1. Sample Size and Power

**Specific Aim 1** We assume that inclusion of 300 children (150 randomized to each arm) will provide 80% power to detect a 27% increase in weight gain (g/kg/day) in children receiving azithromycin compared to children receiving amoxicillin at an alpha of 0.05. Assumptions for this calculation were based on the pattern of weight gain reported in a trial of routine amoxicillin for uncomplicated SAM in Niger comparing children receiving amoxicillin to placebo over time. We assumed an average weight gain of 4.9 g/kg/day in the amoxicillin arm, with a standard deviation of 3.9 g/kg/day, and loss to follow-up of 10%. A 27% increase corresponds to a mean difference in weight gain of 1.3 g/kg/day, or an average weight gain of 6.2 g/kg/day in the azithromycin arm.

This calculation was performed in Stata using the following command:

```
power twomeans 4.9, sd(3.9) alpha(0.05) power(0.8) n(270)
```

**Specific Aim 2.** Inclusion of 300 children (150 randomized to each arm) will provide 80% power to detect an 15 percentage point difference in the proportion of children achieving nutritional recovery in the azithromycin arm compared to the amoxicillin arm. Assumptions for this calculation were based on nutritional recovery reported in the amoxicillin arm of a trial of routine amoxicillin for uncomplicated SAM in Niger. We assumed that 66% of children in the oral amoxicillin arm would achieve nutritional recovery and a loss to follow-up of 10%.

This calculation was performed in Stata using the following command:

```
power twoproportions 0.66, alpha(0.05) power(0.8) n(270)
```

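### The weighted sensitivity analysis for missing outcomes uses baseline variables only, so it cannot detect dropout that follows early weight gain and differs by arm, and its agreement with the complete-case result would falsely reassure.

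*Combined protocol and SAP*

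**What the plan says.** Section 9.2 (Missing data) sets two rules. At or below 10% missing: "of enrolled children is missing outcome data, complete case analyses will be conducted". Above 10%, complete cases are also weighted by the inverse of their estimated probability of being observed, as a sensitivity analysis. The weight model is fixed in advance: "Weights will be constructed with the following baseline characteristics chosen as factors likely to predict follow-up: SES, distance from CSPS, WHZ, and MUAC".

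The Specific Aim 1 model in Section 9.2 is an unweighted linear regression of one enrolment-to-week-8 velocity per child on arm. Sections 9.1 and 9.2 describe no multiple imputation, repeated-measures model or missing-not-at-random analysis, so the weighting step is the only planned check.

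More data are collected than the check uses. Section 2.5 states: "Weight will be measured at all follow-up time points". Section 3.2 places these measurements weekly until recovery and again at week 8. Section 9.1 assumes "loss to follow-up of 10" per cent, which is the same figure as the trigger.

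**The concern.** Inverse-probability weights remove only the selection that their covariates predict. The four listed variables are measured before treatment and are balanced between arms in expectation. They can correct for families who live far away or children who start thinner. They cannot correct for a child who stops attending because the first weeks went badly, unless baseline status predicts those weeks well.

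Dropout that differs by arm is plausible here, though not certain. Families know the allocation (Section 2.3). One arm receives a single observed dose; the other has a 7-day course given mostly at home (Section 4). Weekly visits also end at recovery, which the trial expects to differ by arm.

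What is at stake is the value of the check. If the weighted and unweighted estimates agree because the weights carry no relevant information, a reader will take that agreement as evidence of robustness.

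**Working it through.** **Inputs from Section 9.1.** 300 children, 150 per arm; 270 analysed after 10% loss; SD 3.9 g/kg/day; control mean 4.9; two-sided alpha 0.05; power 80%; target 1.3 g/kg/day.

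**Reproducing the plan's figure.** Minimum detectable difference = (1.960 + 0.842) × 3.9 × √(2/135) = 2.802 × 3.9 × 0.1217 = 1.33 g/kg/day. As a share of 4.9 this is 27.1%, so the stated 27% reproduces.

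**Assumptions (not in the documents).** Percent missing in each arm; how strongly dropout depends on early gain; an early-to-final velocity correlation of 0.7. In the scenarios below poor responders drop out unless stated otherwise. Differences are azithromycin minus amoxicillin.

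**Hand calculation.** In each arm, complete-case bias = share missing × (mean of observed − mean of missing). If missing children gain 0.5 SD less (0.5 × 3.9 = 1.95) in both arms, 5%/15% missing gives 0.05 × 1.95 − 0.15 × 1.95 = −0.195. At 1 SD it gives −0.39. These are 15% and 30% of 1.3. The sign reverses if the heavier loss is in the other arm.

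**Simulation.** 300 children, no true effect, dropout logistic on early gain. Bias in g/kg/day, from a run of 2,000 trials per row:

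| Missing (azithromycin/amoxicillin) and pattern, odds ×2.7 per SD | Complete case | Planned weights | Planned weights + arm | Adding arm × early gain |
|---|---|---|---|---|
| 5%/15%, poor responders leave both arms | −0.23 | −0.23 | −0.22 | 0.01 |
| 5%/15%, response-related in amoxicillin arm only | −0.36 | −0.36 | −0.35 | 0.00 |
| 10%/20%, response-related in amoxicillin arm only | −0.47 | −0.47 | −0.46 | 0.01 |
| 10%/10%, opposite direction by arm | 0.51 | 0.51 | 0.51 | 0.01 |
| 15%/15%, same pattern in both arms | 0.00 (−0.005) | 0.00 | 0.00 | 0.00 |

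For the first pattern, separate runs at odds ×2.7 gave 0.22 to 0.25 in absolute size. At ×4.5 they gave 0.31 to 0.32. As shares of the target: 0.22/1.3 = 17% and 0.32/1.3 = 25%.

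**Milder cases.** The −0.23 at 5%/15% implies a gap of about 0.23/0.10 = 2.3 g/kg/day between observed and missing children. At 8%/12% the same gap gives 0.04 × 2.3 = 0.09. With odds ×1.5, large-sample values are 0.11 at 5%/15% and 0.04 at 8%/12%; one rerun gave as little as 0.02 at 8%/12%.

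**Effect on the error rate.** With a standard error of 0.46 to 0.47, the two-sided rate is P(|Z + bias/SE| > 1.96). Bias 0.22 with SE 0.47 gives 7.5%; bias 0.32 with SE 0.46 gives 10.7%. The nominal rate is 5%.

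**What matters in the weight model.** Adding arm as a main effect, or fitting the baseline weights by arm, moved the bias by at most about 0.03. Adding early gain with its arm interaction brought it close to zero.

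**The case against.** The strongest reply is that the mechanism is possible but undocumented. Both arms receive an active antibiotic, a first dose given by a nurse, the same feeding and the same visits. Treatment differs for 7 days of 56. Eligibility requires catchment residence and availability for 8 weeks, and every child is due back at week 8 whether or not recovered. The trial is a pilot, and it does prespecify a weighted analysis. A threefold imbalance in dropout is an assumption, and milder inputs give a negligible bias. All of this stands, and it limits the size of the point. It does not make the planned weights informative about response-related dropout.

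Three stronger readings are tempting, but the documents do not support them.

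- **That the primary result is biased.** Nothing in the documents says dropout will differ by arm, and response-related dropout of the same kind and rate in both arms gave about no bias.
- **That leaving out treatment arm is the defect.** Arm as a main effect changes almost nothing. The omission that matters is on-study weight together with its interaction with arm.
- **That the 10% trigger causes the problem.** With 10% missing expected, it fired in about 46% of simulated trials, so chance would largely decide whether the check is run. But the planned weights reproduce the complete-case answer, so skipping them loses little. Above 10% the primary result is still complete case.

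**Conclusion.** The point holds as a weakness of the sensitivity analysis, not as a demonstrated error in the primary result. As specified, the weighted analysis would agree with the complete-case analysis in the very situation it should expose.

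The main range, 0.22 to 0.32 g/kg/day, requires unequal loss (5% and 15%), strong dependence on early gain (odds ×2.7 to ×4.5 per SD) and a correlation of 0.7. It falls to about 0.02 to 0.09 at 8%/12% and to near zero with equal, like-for-like dropout. It grows if selection is confined to one arm or runs in opposite directions. The documents also give no figure for how well the four baseline variables predict weight gain; if they predict it well, the planned weights would recover part of the bias.

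The improvement is cheap and worth making before the data are unmasked.

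**What to change.** In Section 9.2 (Missing data):

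1. Build the weights from the four listed baseline variables plus arm, weight-gain velocity (g/kg/day) at the same early visit for every child, and the arm × early-velocity interaction. Week 1 or 2 would serve: recovery needs two consecutive qualifying visits, so weekly follow-up should not end before week 2. State a rule for children lost before that visit.
2. Do not use the last observed weight change as the covariate. For a completer it is the outcome itself; for a dropout it covers fewer weeks. In a 5%/15% simulation it turned a bias of about −0.22 to −0.25 into +0.37, or +0.17 with completers cut at week 7.
3. Acceptable alternatives are visit-by-visit (time-varying) weights, or multiple imputation by arm from the weekly weights.
4. Run this analysis at any level of missingness, and report percent missing by arm.

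The complete-case analysis may remain primary. The change does not correct it; it provides a check against which its robustness can be judged. Dropout driven by weight that was never observed is beyond any weighting, so a short missing-not-at-random analysis would be a useful addition.

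The cost is SAP wording, a little programming and slightly wider intervals (simulated standard error about 0.47 to 0.49, and up to 0.52 in one set of runs, against 0.46 to 0.47 for complete case). No new data are needed.
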